5.1 Grouping Factor

Study Stage: 1=Safety Portion vs 2=Expansion Portion

5.2 Grouping Factor

Disease type: 1=Elderly newly diagnosed AML (assigned treatment Arm A) vs 2=Relapsed/refractory AML vs 3=HMA failure MDS/ AML vs 4=MF

NOTE: HMA failure MDS patients include MDS, CMML and MDS/MPN overlap patients.

NOTE: Disease type groups 2 and 3 are randomized to arm B or C. Disease type 4 only receives single agent (Arm C)

6.0 Enrollment Procedures

The inclusion and exclusion criteria in this study should not have a negative effect on the enrollment of the desired populations.

Target enrollment at NYU Langone Health for this study is a minimum of 40 patients over 3 years. The target accrual goal for the run in safety is each 6 patients in the single (Arm C) and combination Arms (Arms A and B); once the safe use of combined AraC/AZD1775 or single agent AZD1775 is determined, the study will expand to 20-21 subjects in each arm distributed over the study duration of 3 years. An explorative cohort of MF patients (n=7) will be assigned to single agent AZD1775 treatment as in Arm C, however, these patients will not be counted into the statistical analysis for Arm C. Patients will be recruited from the physician participating in this study.

Consenting, screening, and treatment will take place at the NYU Langone Health PCC or participating sub-sites under the supervision of the Site PI. Prospective subjects will receive detailed information regarding this study; its investigational nature, required study procedures, alternative treatments, risks and potential benefits of the study. They will also receive the informed consent document to read. All questions are answered by the PI and qualified research personnel.

The Principal Investigator(s) or their representatives will:

1. Obtain signed and dated informed consent from the potential subject before any study specific procedures are performed (can be obtained by study investigators).
2. Determine patient eligibility; see Section 3.1 and 3.2
3. Submit registration to NYU Langone Health Perlmutter Cancer Center CTO
4. Receive registration confirmation from the NYU Langone Health Perlmutter Cancer Center CTO, including a unique study identification number assigned to the patient that will be distributed to the study team upon registration of the patient.

Recruitment and consenting will take place in a private area such as an exam room to protect the patient's privacy. The informed consent process and documentation follows the established procedures of the NYU Langone Health Perlmutter Cancer Center Clinical Trials Office.

6.1 Use of DataCore/Epic Information for Recruitment Purposes

Although, primary recruitment will be done via participating physicians contacting potential participants; recruitment will also be done utilizing EPIC.

Any recruitment information sent by email will utilize Send Safe email.

Once potential subjects have been identified, the study team will notify the treating physician (TP) that they have patients eligible to participate. Should the potential subjects agree, the study team will provide the subjects with information regarding the next steps for participation.

If a subject requests information regarding opting out of further recruitment for all research, subjects will be directed to contact [contact] or [name].

6.2 Registration Procedures

6.21 General Guidelines

Each patient must sign and date an informed consent form before undergoing any study specific procedure unless a procedure is being performed as part of the patient's standard of care.

Enrollment in the study requires that all inclusion and exclusion criteria have been met. Enrollment occurs upon confirmation of registration from the NYU Langone Health PCC Clinical Trials Office. The following materials must be submitted to the CTO for subject registration:

1. Complete signed and dated informed consent form
2. Complete signed and dated eligibility checklist

3. All supporting documentation verifying each eligibility criterion has been met

Registration will occur within 48 hours of research coordinator receipt of all of the above documents. A written confirmation of enrollment including a unique study identification number assigned by the research coordinator will be disbursed to the study team upon registration.

Once eligibility is verified, a unique patient study number will be issued within 48 hours of receiving all required registration material. The patient will not be identified by name. This is the point, at which, the patient is considered accrued on study.

6.22 Multi-Site Surveillance

As the lead investigator in a multi-site trial, the Principal Investigator is responsible for organizing and conducting monthly teleconferences with all participating sites. The PI will also be responsible for including data from all of the participating sites within the overall trial's quarterly Data and Safety Monitoring report to the DSMC to include minutes from monthly PI teleconferences. Each participating site will be responsible for submitting the results and recommendations from the DSMC's quarterly reviews to their IRB of record at the time of continuing review. Additionally, the NYU Langone Health PCC Clinical Trial Office, Quality Assurance Unit will provide a remote extensive monitoring including real-time review of all eCRFs to ensure completeness and compliance with the protocol (100% source documentation verification). Additionally, a first subject audit is to be completed within four weeks of enrollment.

6.23 Patient Registrations at Additional Sites

Enrollment at additional sites can begin once each site's IRB has approved this protocol, a copy of each site's IRB approval, Citi training certificates, Medical Licenses and signed CVs are provided to NYU Langone Health Perlmutter Cancer Center (PCC) Clinical Trials Office. Once, all required documents are provided to NYU Clinical Trials Office an activation notification will be sent to the PI and research coordinator of that site. Central registration for this study will take place at NYU Langone Health PCC Quality Assurance Unit ([contact]).

Each patient must sign and date an informed consent form before undergoing any study specific procedures unless a procedure is being performed as part of the patient's standard of care. Once a patient has signed consent, each site must notify the NYU Langone Health PCC Quality Assurance Unit and forward a copy of the signed consent to NYU Langone Health PCC Clinical Trials Office within 24 hours.

Enrollment in the study requires that all inclusion and exclusion criteria have been met. Enrollment occurs upon confirmation of registration from the NYU Langone Health PCC Clinical Trials Office. The following materials must be submitted to the Quality Assurance Unit at NYU Langone Health via email ([contact]):

1. Complete signed and dated informed consent form
2. Complete signed and dated informed consent checklist
3. Complete signed and dated eligibility checklist
4. All supporting documentation verifying each criterion has been met.

Registration will occur once the Senior Research Nurse for Quality Assurance conducts a central review of the submitted materials. Once eligibility is verified, a unique subject study number will be issued within 48 hours of receiving all required registration material. This number is unique to the participant and must be written on all data and correspondence for the participant. The NYU Langone Health PCC CTO will return a signed eligibility confirmation worksheet email with the subject's unique study number.

The subject will not be identified by name. This is the point, at which, the patient is considered accrued on study. Protocol treatment should begin within designated timeframe; issues that would cause treatment delays should be discussed with the overall PI, [name]. All screen failures/ineligible subjects, as well as subject's who withdraw consent prior to initiation of protocol therapy must be submitted to the CTO in a manner analogous to the procedures noted above. Applicable source documentation will be required within the corresponding submissions.

Subjects must not start any protocol procedures prior to registration; each participating institution will order the study agent through NYU Investigational Pharmacy.

Each site is responsible for reporting all unexpected problems involving risks to participants or others to NYU Langone PCC Clinical Trials Office and to their IRB as per site institutional policy.

Please email all SAEs to [contact], [name], and the NYU Langone Health CTO QA specialist.

6.3 Safety & Expansion Portions

6.31 Correlative Research

6.311 A mandatory correlative research component is part of this study, the subject will be automatically registered onto this component (see Section 3.17 and 14.0).

6.32 At the time of registration, the following will be recorded:

- Subject has/has not given permission to store and use his/her sample(s) for future research of Acute Myeloid Leukemia or Myelodysplastic Syndrome at NYU Langone Health.
- Subject has/has not given permission to store and use his/her sample(s) for future research to learn, prevent, or treat other health problems.
- Subject has/has not given permission to give his/her sample(s) to researchers at other institutions.

6.33 Treatment on this protocol must commence at a participating institution, NYU Langone Health, under the supervision of a hematologist.

6.34 Treatment cannot begin prior to registration and must begin \leq 14 days after registration.

- 6.35 Pretreatment tests/procedures (see Section 4.0) must be completed within the guidelines specified on the test schedule.
- 6.36 All required baseline symptoms (see Section 10.3) must be documented and graded.
- 6.37a Study drug is available on site.
- 6.37b Blood draw kit is available on site.
- 6.37c Subject questionnaire booklet is available on site; copies are not acceptable for this submission.
- 6.37d Randomization Procedures
- 6.37d1 After the subject has been registered into the study, the values of the grouping factors will be recorded. An elderly newly diagnosed AML subject will be allocated to arm A. A relapsed/refractory AML or HMA failure MDS/ AML subject will be randomized to treatment group arm B or arm C. MF patients will be allocated to Arm C but not included in the statistical analysis for Arm C, rather descriptive response rates will be summarized separately.
- Elderly (age 60+) newly diagnosed AML subjects assigned to Arm A: AZD1775 days 1-5, 8-12 and AraC days 1-5, 8-12
 - Relapsed/Refractory AML and HMA failure MDS/ AML subjects randomized to Arm B: AZD1775 days 1-5, 8-12 and AraC days 1-5, 8-12 or Arm C: AZD1775 days 1-5, 8-12.
 - MF patients allocated to Arm C

7.0 Protocol Treatment

7.1 Pre-Treatment Requirement

7.11

All patients will receive a 5-HT₃ antagonist, ondansetron (Zofran) 8 mg PO QD or granisetron (Kytril) 1 mg PO QD prior to each dose of AZD1775. If nausea and vomiting continue, a second dose of antiemetics can be taken 8 hours later if necessary. In addition, dexamethasone 4 mg PO may be given with each AZD1775 dose unless contraindicated or not well-tolerated. Dexamethasone or the 5-HT₃ antagonist may be given by IV route as needed.

Promethazine (Phenergan), prochlorperazine (Compazine), and benzodiazepine may still be used as additional adjunctive treatments during AZD1775 therapy.

Please note: aprepitant [Emed] and fosaprepitant are not permitted due to known DDIs.

Patients should be encouraged to maintain liberal oral fluid intake.

Suitable alternative medications may be used, with adequate justification, in those studies where the use of any of the above medications might interfere with other study procedures or are deemed insufficient.

7.2 Treatment Plan for AZD1775 combined with AraC (Arms A and B)

7.21 Safety Portion

The safety portion of this trial will consist of a limited dose escalation and subsequently assess the safe combination dose of AZD1775 with standard AraC s.c. twice daily dosing. A limited safety run in dose escalation of AZD1775 will be performed as outlined in Table 7.21. Three subjects from either arm will be treated and observed for a minimum of 28 days to assess toxicities. Toxicity and DLT/MTD criteria will follow a classical three by three dose escalation toxicity assessment:

In the run-in portion of the trial, 3 patients who are eligible for the trial will be treated at dose level 0 (AZD1775 200 mg PO once daily and AraC 20 mg s.c. twice daily days 1-5 & 8-12) and observed for a minimum of 28 days. If there are no DLT defining toxicities, the following 3 patients will be treated at dose level 1 (AZD1775 250 mg PO once daily and AraC 20 mg s.c. twice daily days 1-5 & 8-12). If there are no DLT defining toxicities at dose level 1, the next 3 will be treated at dose level 2 (AZD1775 300 mg PO once daily and AraC 20 mg s.c. twice daily days 1-5 & 8-12). If there are no DLTs in the first 3 patients at dose level 2, an additional 3 patients will be treated. If $\leq 1/6$ patients at dose level 2 experience DLT, the Expansion portion (cohort) of the trial will be opened for the remaining patients.

If 1/3 patient experiences a DLT at a given dose level, an additional 3 patients will be enrolled at this dose level. If there are no further DLTs (maximum of $\leq 1/6$ patients with DLT at any given dose level) this dose level will be defined as the MTD dose level and advanced to the Expansion portion of the study. If 2/3 patients experience a DLT, dose will be de-escalated by one dose level and an (additional) 3 patients treated at the next lower dose level, unless six patients have been treated already and there were $\leq 1/6$ DLT, then this level will be defined as MTD dose level and advanced to the Expansion portion. If $\geq 2/6$ patients experience at any dose level, then enrollment into that study arm will be placed on hold, and a meeting of all participating investigators, the NYU DSMC Medical Monitor, the Astra Zeneca Trial/ Program Lead will be called to determine how best to proceed, as well as available PK data will be reviewed.

If DLT occurs at dose level 0, study will be de-escalated to dose level -1 (AZD1775 150 mg PO once daily and AraC 20 mg s.c. twice daily days 1-5 & 8-12). If $\leq 1/3$ patients have DLT another 3 patients will be enrolled and if $\leq 1/6$ patients have DLT, then this level will be

defined as MTD dose level and advanced to the Expansion portion. If 2/3 patients at dose level -1 have DLT, the combination will be deemed as not tolerable in combination with LD-AraC.

NOTE: the Safety/ Escalation portion and MTD determination for Arm A (newly diagnosed/ untreated AML) and Arm B (relapsed/ refractory AML, HMA failure MDS) as outlined above will be performed together with patients from both Arms eligible. .

Table 7.21: Safety run in dose escalation

Dose Level	AZD1775 ²	Cytarabine (AraC) ¹
-1	150 mg PO once daily days 1-5 & 8-12	20 mg SC twice daily days 1-5 & 8-12
0	200 mg PO once daily days 1-5 & 8-12	20 mg SC twice daily days 1-5 & 8-12
1	250mg PO once daily days 1-5 & 8-12 ¹	20 mg SC twice daily days 1-5 & 8-12
2	300 mg PO once daily days 1-5 & 8-12	20 mg SC twice daily days 1-5 & 8-12

¹ AraC dose is a fixed dose of 20 mg s.c. per a single dose twice daily.

² AZD1775 should be taken either 2 hours before or 2 hours after a meal.

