Despite a lack of a clear biomarker/ PD marker for WEE1 kinase inhibition, based on preclinical data an effective pharmacological dose is up to the range of 750 nM, possibly higher to maximally 1000 nM. From recent PK data (REFMAL 984 and NCI study), daily dosing for 5 days for one or two weeks with AZD1775 was determined as the RP2D, that yielded an AUC (0-8 hrs) of ~8000nM. Therefore we would expect that 300mg AZD1775 daily would yield around 600-800 to maximally 1000 nM concentrations of AZD1775 in the first 8 hours.

For the combination arms (Arms A and B) in the Escalation portion we will escalate dose starting at AZD1775 200 mg daily on a 5-2-5 schedule. We will escalate up to/ until

- a) the current MTD/ RP2D of 300 mg daily (5-2-5 schedule) is reached at acceptable toxicity (AEs) regardless of preclinical PK efficacy
- b) DLT defining toxicities/ AEs are observed
- c) clinical efficacy is observed that would meet the primary response endpoint already below the current RP2D of 300 mg AZD1775 daily
- d) Clinical PK (AUC) of AZD1775 reaches approx. > 1000 nm/ hr

We will accomplish above goals with real-time assessment of safety, efficacy, PK and/or PD in each cohort.

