7.5 MTD Determination

This MTD determination applies to the Safety Portion. MTD for the safety portion will be defined as the dose level below the lowest dose that induces dose-limiting toxicity in at least one-third of subjects (at least 2 of a maximum of 6 subjects).

- 7.51 Three subjects will be treated at a given dose level combination and observed for one cycle to assess toxicity (accrual will be suspended while the 3 subjects are treated and observed – only applicable to the dose escalation cohort/ part of study).
 - 7.52 If DLT is not seen in any of the 3 subjects or in 1 of 3 subjects, 3 new subjects will be accrued and treated at the same dose level (accrual will be suspended while the 3 subjects are treated and observed). If DLT is seen in 2 or 3 of 3 subjects treated at a given dose level, then the next 3 subjects will be treated at the next lower dose level, if only 3 subjects were enrolled and treated at this lower dose level.
 - 7.53 After enrolling 6 subjects on a specific dose level, if DLT is observed in 1 or less subjects, then the combination dose will be considered safe for the expansion phase. If DLT is observed in at least 2 of 6 subjects, then the MTD will have been exceeded and defined as the previous dose unless only 3 subjects were treated at the lower dose level. In that case, 3 additional subjects will be treated at this lower dose level.
 - 7.55 If a subject fails to complete one cycle of treatment for reasons other than dose-limiting toxicity defined adverse events, the subject will be regarded as non-informative for estimating the MTD and an additional subject will be treated at the current dose level.
- 7.6 Dose escalation (inpatient) will not be allowed for a subject.
- 7.7a For this protocol, the subject must return to the consenting institution for evaluation at least once per cycle.
- 7.7b Local Medical Doctor (LMD)
When it has been determined that a patient's malignant disease is stable or objective tumor regression has been observed and the patient is tolerating therapy without excessive toxicity, after the first cycle of treatment, the standard of care drug AraC may be administered by the patient's Local Medical Doctor

(LMD). However, study drug AZD1775 can only be dispensed by an investigator or investigational site of the study. The registering physician retains responsibility for the patient.

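### Three dose rules in the safety portion are wrong or in conflict as written: one DLT in three at 200 mg in the combination, Arm C's de-escalation trigger, and the action at two or more DLTs in six

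*Combined protocol and SAP*

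**What the plan says.** **Combination (Arms A and B), Section 7.21.** The run-in starts at 200 mg (level 0 of Table 7.21), with 250 and 300 mg above it and 150 mg below.

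- At 0/3: "If there are no DLT defining toxicities, the following 3 patients will be treated at dose level 1".
- At 1/3: "If 1/3 patient experiences a DLT at a given dose level, an additional 3 patients will be enrolled at this dose level". With no further DLT, that level is the MTD.
- At 2/3: go down one level and treat three there, unless six were already treated there with at most one DLT.
- At 2/6 or more: "patients experience at any dose level, then enrollment into that study arm will be placed on hold", and a meeting is called.
- The level-0 paragraph then says: "If DLT occurs at dose level 0, study will be de-escalated to dose level -1 (AZD1775 150 mg PO once daily".

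**All arms, Section 7.5.** Section 7.52: "If DLT is not seen in any of the 3 subjects or in 1 of 3 subjects, 3 new subjects will be accrued" at the same dose. Section 7.53, at 2/6 or more: "the MTD will have been exceeded and defined as the previous dose unless only 3 subjects were treated at the lower dose level"; if so, three are added at the lower dose.

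**Arm C, Section 7.31.** At most 1/6 makes a dose the MTD. De-escalation from levels 0, -1 and -2 is triggered by at most 2/6. A later sentence puts a level on hold, with a meeting, at 2/6 or more. No action is given for 1/3 or for 2/3 or more at the 300 mg starting dose.

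**Section 16.7.** At two or more DLTs in the first six, reduce the dose as Section 8.0 defines and treat another six. De-escalation runs to level -2; beyond that the study closes for evaluation and may re-open.

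**Section 8.11.** The combination scale starts at 300 mg as level 0. Its lowest step is 200 mg with AraC 10 mg.

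**The concern.** Each regimen should have one action per DLT count. In three places a site applying the text would find two actions, or the wrong one.

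1. **1/3 at 200 mg, combination.** One paragraph stays at 200 mg and adds three; another leaves for 150 mg.
2. **Arm C trigger.** As printed, 0/6 and 1/6 both accept the dose and de-escalate from it, and 3/6 or more meets no de-escalation rule.
3. **2/6 or more.** Section 7.21 holds and meets, Section 7.53 falls back to the previous dose, and Section 16.7 reduces on another scale. Nothing says which comes first, and the next cohort is three or six.

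These rules set the next patient's dose and the dose taken into expansion.

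**Working it through.** **Inputs.** The rules are from Sections 7.21, 7.31, 7.5, 8.11, 16.7 and 16.8. The documents give no expected DLT rate, so rates are assumed: 10/20/30% for single-dose figures, and three sets for the whole path, at 150/200/250/300 mg: S1 = 5/10/15/20%, S2 = 20% throughout, S3 = 10/20/30/40%.

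**The plan's own figure.** Section 16.8 gives 0.85 as the posterior probability that the DLT rate exceeds 20% after 2 of 6 with a Beta(1,1) prior. The posterior is Beta(3,5), and P(rate > 0.20) = 0.852. It reproduces.

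**Binomial pieces.**

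| DLT rate | P(0/3) | P(1/3) | P(≥2/3) |
|---|---|---|---|
| 10% | 0.729 | 0.243 | 0.028 |
| 20% | 0.512 | 0.384 | 0.104 |
| 30% | 0.343 | 0.441 | 0.216 |

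**Part 1: 1/3 at 200 mg.** The rules give different doses when 1/3 is followed by 0/3: the counted rule expands at 200 mg, the uncounted one has already gone to 150 mg.

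P(1/3) × P(0/3): 0.243 × 0.729 = 0.177; 0.384 × 0.512 = 0.197; 0.441 × 0.343 = 0.151.

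For the whole path, P(expand at 150 mg) = P(leave 200 mg for 150 mg) × P(150 mg accepted). Acceptance needs at most 1/6: P(0/3) × P(≤1/3) + P(1/3) × P(0/3) at the 150 mg rate. The counted rule leaves at ≥2/3; the uncounted rule leaves at ≥1/3. A count of 2/6 or more is treated as a hold.

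| Set | Accept at 150 mg | Counted rule | Uncounted rule |
|---|---|---|---|
| S1 | 0.967 | 0.028 × 0.967 = 0.027 | 0.271 × 0.967 = 0.262 |
| S2 | 0.655 | 0.104 × 0.655 = 0.068 | 0.488 × 0.655 = 0.320 |
| S3 | 0.886 | 0.104 × 0.886 = 0.092 | 0.488 × 0.886 = 0.432 |

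**Part 2: Arm C.** With six patients treated, at 10/20/30%:

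- P(≤1/6), where acceptance and the printed trigger both apply: 0.886/0.655/0.420.
- P(≥3/6), where no de-escalation rule applies: 0.016/0.099/0.256.

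With the sign corrected, the outcome at 300 mg that meets both the step-down and the hold, with three added after 0/3 or 1/3, is P(0/3) × P(≥2/3) + P(1/3) × P(≥1/3) = 0.086/0.241/0.364.

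**Part 3: 2/6 or more in the combination.** Next dose on each scale:

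| From | Table 7.21 | Section 8.11 |
|---|---|---|
| 300 mg | 250 mg | 250 mg |
| 250 mg | 200 mg | 200 mg |
| 200 mg | 150 mg, AraC 20 mg | 200 mg, AraC 10 mg |

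Only the last row differs. Under the counted rule, 2/6 or more at 200 mg arises in two ways: 1/3 then at least one more; or 0/3, failure at 250 mg (≥2/3), return to 200 mg, then ≥2/3.

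- S1: 0.0659 + 0.729 × 0.061 × 0.028 = 0.067
- S2: 0.1874 + 0.512 × 0.104 × 0.104 = 0.193
- S3: 0.1874 + 0.512 × 0.216 × 0.104 = 0.199

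In Arm C at 200 mg (level -2), Section 7.31 continues to 150 mg (level -3), while Section 16.7 stops for evaluation.

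**Minor: 0/3 at 200 or 250 mg.** Section 7.21 escalates; Section 7.52 adds three. The three extra patients would show two or more DLTs at 200 mg with probability P(0/3) × P(≥2/3) = 0.020/0.053/0.074, so the effect on dose is small.

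**The case against.** **Part 1 has a natural reading.** Section 7.21 announces a classical three-by-three scheme, and its 1/3 rule covers any level. The level-0 sentence may only be naming the dose to use once 200 mg has failed. That is probably what was meant, and a literal reading errs toward the lower dose. But the sentence does not say so, and the sentences right after it do give counts.

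**The Arm C sign is a slip with a known answer.** Sections 7.53 and 16.7 both use two or more of six, and Section 7.31 prints it correctly once. Agreed. Correcting it still leaves step-down and hold-with-meeting at the same count. The hold there is on the dose level, so it is compatible with stepping down, but the order is not stated.

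**Hold-and-meet can precede a step down.** Also true. The different cohort sizes and lowest levels remain.

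Four stronger readings are tempting but not supported:

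- *The plan might expand at a dose with two or more DLTs in six.* No section does; Section 7.31's hold also catches 3/6 or more.
- *The conflict over the next dose affects 0.27/0.38/0.44 of trials.* Those are the probabilities of 2/6 or more at any dose under S1 to S3. The scales differ only from 200 mg.
- *Section 7.52 shows that the combination should not escalate after 0/3.* Section 7.4.b says "we will escalate dose starting at AZD1775 200 mg daily on a 5-2-5 schedule", Section 7.5 defines the MTD as "MTD for the safety portion will be defined as the dose level below the lowest dose that induces dose-limiting toxicity in at least one-third", and Section 7.53 allows for only three patients at the lower dose. Escalation is intended.
- *The efficacy tests become invalid.* Section 16.21 ties evaluability to the MTD, but Sections 16.22 and 16.23 do not. Whichever dose is chosen, the binomial rules keep their stated error rates.

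Section 16.8 only says that termination will be considered, under a heading on ongoing monitoring, so it is at most a point to clarify.

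**Conclusion.** The concern holds for three rules, and they must be corrected because they govern the next patient's dose. The level-0 sentence in Section 7.21 contradicts the 1/3 rule in the same section and Section 7.52. The Arm C trigger in Section 7.31 has the wrong sign. The actions at 2/6 or more are unordered, use different cohort sizes and, from 200 mg, point to different next doses.

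Part 1 is the largest in the combination: 15 to 20% of trials at DLT rates of 10 to 30% reach the outcome on which the two rules give different doses. The next-dose conflict in Part 3 has probability 0.067 to 0.199. All these sizes rest on assumed DLT rates; the contradictions themselves do not. The scope of Section 7.52 at 0/3, the level label for 200 mg in Section 7.31 and the reach of Section 16.8 are minor. The consequence is which dose patients receive and which dose is expanded.

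**What to change.** Put one mutually exclusive decision table per regimen in Section 7, cited by Sections 7.21, 7.31, 7.5 and 16.7.

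**Combination**

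| Outcome | Action |
|---|---|
| 0/3, first three at 200 or 250 mg during escalation | Escalate |
| 0/3 at 300 mg, at 150 mg, or at any level reached by de-escalation | Add three; do not re-escalate |
| 1/3 | Add three |
| 0/6 or 1/6 | Accept as MTD |
| ≥2/3 | Down one level of Table 7.21; if six were already treated there with ≤1/6, that level is the MTD; at 150 mg, stop |
| ≥2/6 | One stated hold-then-de-escalate sequence |

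Change the level-0 sentence in Section 7.21 to require at least two DLTs.

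**Arm C.** Change the trigger in Section 7.31 to two or more of six at every level. State whether the hold and meeting come before the step down. At 300 mg, add three after 1/3 and de-escalate after 2/3 or more.

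**Section 16.7.** Cite Tables 7.21 and 7.31 instead of Section 8.0, with one cohort size and 150 mg as the lowest level.

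**Minor.** Limit Section 7.52's add-three at 0/3 to the cases in the second row and to Arm C. Relabel 200 mg as level -2 in Section 7.31. State whether Section 16.8's 2-of-6 boundary applies in the run-in.

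The sponsor's clinical team must confirm the action at 2/6 or more. The cost is amendment wording only, with no added patients or visits.
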